9 OBJECTIVES AND OUTCOME MEASURES

9.1 Aim

The primary aim of the study is to establish whether ACL repair provides more benefit than ACL reconstruction in patients with recent proximal ACL ruptures of the knee.

Research Question

Does acute ACL repair provide superior clinical outcomes (as measured by the Knee injury and Osteoarthritis Outcome Score (KOOS-4)) at 24 months, and is it cost effective compared to ACL reconstruction in patients with recent proximal ACL ruptures?

Primary and Secondary objectives/outcomes measures

The primary and secondary objectives are outlined below in Section 9.2. The primary outcome measure is the aggregated and averaged score of four of the five sub-scales of KOOS (KOOS-4): pain, symptoms, activities of daily living, and sport and recreation function, at 24 months post randomisation. The secondary outcomes are the five individual KOOS sub-scale scores (KOOS-5), repair/ graft re-rupture rate, re operation, health-related quality of life, time to return to work, time to return to sport, emotional functioning and cost effectiveness (including time away from paid employment and education). Measures include KOOS at 6 and 12 months post-randomisation and over the 24 months period, complications, graft failure, re-operation, EQ-5D-5L, emotional functioning questions taken from KQoL-26, post operative pain, and resource usage. A subjective measure will also be collected on the Surgery CRF to understand 'surgeon confidence' in the ACL surgery performed (recorded on a scale of 1-10).

Activity level will be assessed using the Tegner Scale, graded from 1 (low activity levels) to 10 (professional level). In addition, the Tegner has been modified as follows: three columns with the headings of (1) activity level before your injury, (2) current level of activity (today) and (3) level you expect to return to, were added to the baseline form. At 6, 12 and 24 months, the Tegner contains one answer column as follows: current level of activity (today).

_

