9.3 Secondary objectives and outcome measures

Objective	Outcome measure	Time point(s) of evaluation of this outcome measure (if applicable)	Data required	Source data (including location)
Evaluate outcomes related to the knee and changes to scores over time	KOOS score (all five KOOS domains will be quantified at each time point)	6, 12 and 24 months after randomisation	KOOS Questionnaire	Follow-up questionnaires. Completed by participants either on paper or entered directly into REDCap.
Determine the cost- effectiveness of ACL repair compared to	Resource use data (participant reported questionnaire and clinician reported i.e. surgery and rehabilitation data, complications/readmissio	6, 12 and 24 months after randomisation	 Health Economics Questionnaire EQ-5DL & -VAS Questionnaire 	Follow-up questionnaires. Completed by participants either on paper or entered

ACL reconstructio n in patients with recent proximal ACL ruptures	ns, including length of procedure, complication rate; reoperation rate). EuroQol (EQ-5D-5L and EQ-VAS)		Case Report Forms: • Surgery • InPatient • Complications	directly into REDCap. Case Report Form (where the data is not recorded directly anywhere else first) Hospital records (from which data will be summarised into the CRF)
To assess patient emotional functioning following ACL repair or reconstruction surgery	Emotional functioning questions (6 item questionnaire taken from KQoL-26)	Baseline, 6, 12 and 24 months after randomisation	• Emotional Functioning Questionnaire	Follow-up questionnaires. Completed by participants either on paper or entered directly into REDCap.
To assess surgeon confidence in the ACL surgery performed	Surgeon confidence (a single question with the answer recorded on a scale of 1-10)	Day of Surgery	• Surgery Case Report Form	Case Report Form
To determine levels of post-operative pain at 3- and 6-weeks following ACL repair and reconstruction	Post operative pain score	3 and 6 weeks after randomisation	• Pain NRS	Follow-up questionnaires. Completed by participants either on paper or entered directly into REDCap.
To assess return to activity / level of sports following ACL repair or reconstruction surgery	Modified Tegner score Tegner score	Baseline 6, 12 and 24 months after randomisation	 Modified Tegner Questionnaire Tegner Questionnaire 	Follow-up questionnaires. Completed by participants either on paper or entered directly into REDCap.

	T				

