10.2 Collection of outcome data and follow-up assessments

The flow of the patients through the study and outcome collection timepoints is outlined in the flow diagram (Appendix 1). The patient self-reported questionnaire will include the outcomes indicated above and will be completed by participants at baseline, 6, 12 and 24 months (computer-based / e-mail /paper-based) depending on patient preference) post randomisation and collected by a web-

based platform (REDCap) developed and maintained by the CTU (OCTRU). Data on post operative pain will be collected at 3- and 6-weeks post randomisation via SMS message link /email link or post and recorded in REDCap.

Refer to Section 17 for full details of outcome data collection and follow-up assessments.

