17.2 Data Collection

17.2.1 Baseline

Baseline assessments may be completed in the outpatient clinic, pre-operative assessment clinic, designated research clinics or on the ward during admission for surgery. Patient demographics will be captured at baseline and in part used to describe the population included and assessed to evaluate equality, diversity, and inclusion of participants taking part. The KOOS, EuroQol EQ-5D-5L, emotional functioning questions taken from KQoL-26 and Modified Tegner, collated as a Baseline Questionnaire, will be collected prior to randomisation. Ideally, the Patient-Reported Outcome Measures (PROMs) will be completed in clinic but, if the participant requests to complete the PROMs outside of clinic (either on paper or electronically), this is permissible, but they will have to return the completed form to site staff prior to randomisation.

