23.3.2 Secondary outcome(s)

Secondary outcomes will be analysed in a similar manner to the primary outcome. KOOS over 24 months, EQ-5D-5L and EQ-VAS, emotional functioning questions taken from KQoL-26, and postoperative pain will use mixed-effects linear regression, like that of the primary outcome, that also incorporates a time-by-treatment effect as a fixed effect and patient as a random effect. All five KOOS domains will be quantified at each time point. Pain-NRS at 3 and 6 weeks will be analysed using a simpler multiple linear regression model adjusted for site using robust variance. Modified Tegner will be compared at each time point in a similar manner. Graft failure and re-operation will be analysed using survival analysis methods: Kaplan-Meier curves, and Cox proportional hazards models (or logrank test if insufficient events). The Cox model will be adjusted with mixed-effects, in line with the analysis approach for other outcomes, if there are enough events. If not, the model will be unadjusted⁽⁴⁵⁾. Patient satisfaction questions will be analysed using logistic regression and adjusted for minimisation factors in line with other outcomes. Intervention-related complication (up to 24 months) will be presented using descriptive statistics, by type, frequency and treatment arm.

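### Section 23.3.2 gives the 3- and 6-week pain score two different models, one omitting two minimisation factors, and names a baseline-only form for the activity comparison

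*Protocol*

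**What the plan says.** Protocol section 23.3.2 lists the outcomes for a longitudinal model and ends the list with pain: "and postoperative pain will use mixed-effects linear regression, like that of the primary outcome, that also incorporates a time-by-treatment effect as a fixed effect". The patient is the random effect. Two sentences later it says "Pain-NRS at 3 and 6 weeks will be analysed using a simpler multiple linear regression model adjusted for site using robust variance". The next sentence is "Modified Tegner will be compared at each time point in a similar manner". Further on, the paragraph says that patient satisfaction will be adjusted for the minimisation factors, as the other outcomes are.

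On measurement, section 10.2 says "Data on post operative pain will be collected at 3- and 6-weeks post randomisation". The matching objective in section 9.3 is "To determine levels of post-operative pain at 3- and 6-weeks following ACL repair and reconstruction". Section 17.2.1 lists the baseline instruments, with no pain rating scale among them: "The KOOS, EuroQol EQ-5D-5L, emotional functioning questions taken from KQoL-26 and Modified Tegner, collated as a Baseline Questionnaire, will be collected prior to randomisation". Section 9.1 describes the Tegner modification as three columns on the baseline form, and then says of follow-up: "At 6, 12 and 24 months, the Tegner contains one answer column as follows: current level of activity (today").

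The minimisation factors in section 15.3 are pre-injury Tegner group (0-6, 7-10), planned lateral extra-articular procedure (LEP) and site.

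**The concern.** Two sentences in one paragraph prescribe different analyses of the same data. The two models differ in covariates, in how they treat two ratings from one patient, and in the treatment contrasts they produce. With no main analysis named, the choice stays open. Pain ratings are complete six weeks after each randomisation, so they accumulate early. Section 23.1 has the study statistician write the SAP, and Table 2 in section 18.1 lists that statistician as unblinded. The choice is better fixed now than later. Nor is pain peripheral: the lay summary in section 5 says the patient groups saw the study as important particularly for measuring it.

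The site-only adjustment is a separate matter. Balancing on a prognostic factor and then leaving it out of the model overstates the standard error, so information already collected is not used.

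For activity, the form named in the analysis sentence has no post-randomisation data. The sentence also does not settle which covariates apply.

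**Working it through.** **Same data, two models.** Sections 9.3, 10.2 and 17.2.2 and Table 1 all define post-operative pain as the numerical rating scale at 3 and 6 weeks. The KOOS pain subscale does not explain the double entry, because KOOS is listed separately in the mixed-model sentence. The two specifications are:

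- Mixed model: time-by-treatment term, patient random effect, otherwise like the primary model. Section 23.3.1 gives that model planned LEP, site and the baseline value of the outcome, but not Tegner group. No baseline pain rating exists to serve as the baseline value.
- Linear regression: site only, robust variance. Two of the three minimisation factors (pre-injury Tegner group, planned LEP) are absent.

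**Tegner form.** Table 1 marks the Modified Tegner once, at baseline. A separate Tegner row is marked at 6, 12 and 24 months, and section 17.2.2 puts the Tegner in the follow-up questionnaires. The similar manner of analysis can refer to the pain regression just before it (site only) or to the opening rule of section 23.3.2 (like the primary outcome, so planned LEP, site and an unspecified baseline value). Neither reading names pre-injury Tegner.

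**Cost of site-only adjustment.** The protocol gives no SD for pain or Tegner and no covariate strength, so this is an illustration under assumptions.

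1. Number analysed, from section 23.2. The stated total reproduces: 105 per arm for 9 points, SD 20 and 90% power by non-central t; 210 × (1 − 0.37²) / 0.85 = 210 × 0.8631 / 0.85 = 213.2, against 214. With 15% missing, 214 × 0.85 = 182 analysed.
2. Assumptions: 20 sites; half the patients in each Tegner group; 30% with planned LEP; minimisation with probability 0.8 of the balancing arm after 10 random allocations; treatment effect 0.4 SD; the two omitted factors sharing their explained variance equally; 1,500 runs; linear regression with robust variance.
3. Results:

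| Variance explained by omitted factors | Type I error, site only | Type I error, all factors | Power, site only | Power, all factors |
|---|---|---|---|---|
| 0% | 5.7% | 5.6% | 75% | 75% |
| 10% | 4.2% | 5.1% | 77% | 80% |
| 30% | 1.6% | 3.6% | 79% | 88% |

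The simulation standard error around a 5% rate is √(0.05 × 0.95 / 1500) = 0.56 percentage points. The 3.6% is therefore about 2.5 standard errors below 5%, and the table should not be read to the last decimal.

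4. Check by hand for the 30% row. If minimisation balances the omitted factors, the estimate varies with only 70% of the variance, while the site-only standard error still carries 100%. The effective critical value is 1.96 / √0.7 = 2.34, which gives a two-sided error of about 1.9%, near the simulated 1.6%. The mean standard errors were 0.151 (site only) and 0.127 (all factors). Site-only power is then about Φ((0.4 − 1.96 × 0.151) / 0.127) = Φ(0.82) = 79%.

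**The case against.** The strongest reply is that nothing here blocks an analysis, and most of it stands. A reader might infer that the two outcomes cannot be analysed correctly as written. The documents do not support that. Either pain model can be fitted to two time points and gives a valid comparison. Current activity is collected at 6, 12 and 24 months, and no one would take a pre-randomisation form as an outcome, so the Tegner wording is a naming slip.

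A reader might also infer inflated false-positive risk from testing weeks 3 and 6 separately. Section 23.3.2 does not say that the weeks are tested separately, and section 23.3 sets a nominal 5% level throughout. The mixed model with a time-by-treatment term would yield week-specific effects too, so choosing it would not settle that question.

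Nor do the documents show that the Tegner comparison is adjusted for site only; that is one of two readings. Pre-injury Tegner group is also absent from the primary model in section 23.3.1, so its absence is not peculiar to these outcomes.

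Finally, the pain-scale sentence is the more specific of the two, and the lack of a baseline rating is a plausible reason for a simpler model. Keeping it and removing pain from the mixed-model list would resolve the contradiction just as well. What remains is that the protocol does not make that choice, and that its site-only model conflicts with the paragraph's own reference to minimisation factors. These are stated contradictions, not detail left to the SAP.

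**Conclusion.** The point holds as a contradiction and an under-adjusted model in two secondary outcomes. The pain ratings have two specified models with no main one. The pain regression leaves out two of the three minimisation factors. The activity sentence names a form collected only at baseline and leaves its covariates ambiguous.

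The omission does not bias the treatment estimate, and it makes the test conservative rather than liberal. Its cost runs from nothing, if the omitted factors are not prognostic, to about 9 percentage points of power (88% to 79%) if they explain 30% of the variance. That range rests wholly on the simulation assumptions; the protocol gives no figure for the strength of these factors in pain or activity. The primary analysis and the sample size of 214 are unaffected.

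**What to change.** In section 23.3.2, and in the SAP to match:

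- Name one main model for the pain rating at 3 and 6 weeks. Remove the other or label it a sensitivity analysis. Either model can be the main one.
- Replace Modified Tegner with current Tegner level at 6, 12 and 24 months.
- State the covariates for both outcomes: pre-injury Tegner, planned LEP and site. For the Tegner outcome, use the pre-injury level from the baseline form.
- Optionally, add baseline KOOS pain as a covariate for pain, since there is no baseline rating. This is a matter of preference.

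The cost is wording only, because every variable is already collected. The change should be made before outcome data are compared by arm.

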Time to return to sport To assess patient satisfaction with the outcome of treatment following ACL repair or reconstruction surgery	Patient satisfaction: 2 questions, Likert scale: 1. Would you have the treatment again if you could go back 2. Assessment of knee after versus before (is it better?)	12 and 24 months after randomisation 12 and 24 months after randomisation	 Return to Sport Questionnaire Patient Satisfaction Questionnaire 	Follow-up questionnaires. Completed by participants either on paper or entered directly into REDCap.	
To assess the complication co	Intervention related complications including re-operation	6, 12 and 24 months after randomisation Operative Postoperativel y up to 24 months after randomisation Review at the 24-month time point.	 Health Economics Questionnaire Case Report Form. 	Case Report Form (where the data is not recorded directly anywhere else first) Hospital records (from which data will be summarised into the CRF)	
	Objective evidence of graft/repair failure (defined on clinical assessment, imaging or operative assessment	Up to 24 months after randomisation	• Case Report Form.	Hospital records (from which data will be summarised into the CRF)	

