17.6 Withdrawal

Withdrawal of consent means that a participant (and/or their parent/guardian) has expressed a wish to withdraw from the study altogether or from certain aspects of the study only. The type of withdrawal will be collected on the CRF labelled 'Withdrawal'.

Participants may also be withdrawn from the study (or aspects of the study) by their clinician if they believe the participant needs to be withdrawn.

The Withdrawal CRF should be completed to document the reasons for withdrawal and state who the decision to withdraw was made by. Discussions and decisions regarding withdrawal should be documented in the participant's medical notes. Investigators should continue to follow up any SAEs and should continue to report any SAEs to resolution in the CRF in accordance with the safety reporting section.

Where a participant expresses a wish to withdraw from the study, the research team will determine which aspect(s) of the study the participant wishes to withdraw from.

The aspects of the study that the participant may request to withdraw from are as follows:

- No longer willing to have surgery
- No longer willing to complete study questionnaires
- No longer willing to attend study visits
- No longer willing to be contacted by the research team to obtain CRF/outcome data
- No longer willing to have routine data from the medical record provided to the study
- No longer willing for routine data from health data providers e.g. NHS England, to be provided to the study

Where a participant wishes to withdraw from all aspects of study participation detailed above this will be recorded on the Withdrawal CRF as full withdrawal.

In addition to participant self-withdrawal, an investigator may decide to withdraw a participant from study intervention for clinical reasons or other reasons such as non-compliance, eligibility. Participants and their parent/guardian will still be asked to participate in the collection of follow-up data. The reason for withdrawal will be recorded on the study withdrawal case report form.

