21.3 Expected adverse events

The expected adverse events related to the procedures are outlined below, and will be collected as complication data on CRFs, separating intra-operative complications, post-operative pre-discharge complications, and post-discharge complications. All complications will be graded using a standard classification, 'The Clavien-Dindo Classification of Surgical Complications' (38). Participants will be informed of the standard risks associated with the anaesthetic and the surgical procedure.

All ACL repair or reconstruction procedures whether primary surgery or revision carry a risk of
anaesthesia related problems which can include death, morbidity including wound infection,
bleeding intra and post operatively, pulmonary embolism (PE), deep vein thrombosis (DVT),
confirmed cerebrovascular accident (CVA), confirmed myocardial infarction (MI), and
complications secondary to existing comorbidity e.g. ischaemic heart disease, septicaemia, the
need for blood transfusion and revision operation.

² Medical events that may jeopardise the participant or may require an intervention to prevent one of the above characteristics/consequences.

- Specific complications following both ACL reconstruction and ACL repair procedures include:
 patella fracture, patella tendon avulsion, anterior knee pain, vascular injury and bleeding,
 femoral tunnel blowout, nerve damage (including numbness or weakness), complex regional
 pain syndrome, lack of extension/fixed flexion deformity, stiffness, infection, graft failure and
 continued instability, delayed wound healing, continued or worsened pain, fracture,
 compartment syndrome, swelling, additional contralateral graft harvest (reconstruction-only)
 and newly acquired meniscal pathology.
- Specific complications following rehabilitation include continued instability and subsequent newly acquired meniscal pathology causing pain. These complications may result in the need for further surgery.

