21.5 Procedure for collecting safety events from sites/participants

Details of all complications will be collected and recorded as detailed in Section 21.3. A final readmission checklist will be undertaken by the Research staff on hospital records at 24 months post randomisation to ensure that all complications data is collected from participants (i.e. those who had not returned a questionnaire). Data from readmission events identified will be recorded in the CRF.

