23.7 Level of Statistical Significance

All treatment comparisons will be reported with 95% confidence intervals and a significance level of 5% will be used to test statistical significance.

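### Intervention-related complications are planned as descriptive figures only; one participant-level risk difference with a 95% CI would be a cheap improvement

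*Protocol*

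**What the plan says.** Table 9.3 of the protocol lists "Intervention related complications including re-operation" among the secondary outcome measures, and gives objective graft or repair failure a row of its own.

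Section 23.3.2 then treats the parts differently. "Graft failure and re-operation will be analysed using survival analysis methods", with Kaplan-Meier curves and a Cox model, or a log-rank test if events are few. For the rest, "Intervention-related complication (up to 24 months) will be presented using descriptive statistics, by type, frequency and treatment arm".

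Three general statements bear on this without naming complications:
- Section 23.3.2 opens by saying that secondary outcomes follow the approach used for the primary outcome.
- Section 23.3.1 says that results will be given as an estimate with a 95% CI where that can be done.
- Section 23.7 says: "All treatment comparisons will be reported with 95% confidence intervals".

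On data collection, section 21.3 separates intra-operative, pre-discharge and post-discharge complications and says: "All complications will be graded using a standard classification". Table 1 places the first two kinds on the Surgery and InPatient CRFs. Sections 17.2.2 and 21.5 add a check of hospital records at 24 months.

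**The concern.** Section 8 gives fewer surgical complications as one of the possible advantages of repair over reconstruction. A reader of the final report will therefore look for what the trial found on this. Under the stated method the reader sees counts by type and arm. No planned figure shows how large a difference in complications the data are compatible with, or can exclude. A small imbalance could then be read as reassurance or as a warning when it supports neither.

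The promise of intervals in section 23.7 does not clearly close the gap, because it applies to treatment comparisons and none is planned for these complications. An interval added later without being specified in the SAP would count as a non-planned analysis, which section 23.3 says will be labelled post hoc.

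**Working it through.** **What the text fixes.** The methods named in section 23.3.2 are:

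| Outcome | Between-arm method |
|---|---|
| KOOS over time, EQ-5D-5L, EQ-VAS, emotional functioning, post-operative pain, Tegner | mixed or linear regression |
| Graft failure, re-operation | Kaplan-Meier, Cox or log-rank |
| Patient satisfaction | logistic regression |
| Other intervention-related complications | none; descriptive by type, frequency and arm |

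This is a method the protocol states, so it is not simply a detail left to the SAP.

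**Number available.** The protocol gives no figure for complications. Its only design figure is the KOOS-4 sample size, which reproduces. For 9 points, SD 20 and 90% power, the non-central t calculation gives 105 per arm. Multiplying by 1 − 0.37² = 0.8631 gives 90.63, and dividing by 0.85 gives 106.6. Rounding up gives 107 per arm, or 214 in all.

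**Precision of a risk difference at 107 per arm.** All risks below are assumptions. The Wald half-width is 1.96 × √{[p₁(1 − p₁) + p₂(1 − p₂)] / 107}.

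- 10% v 5%: 1.96 × √(0.1375/107) = 7.0 points
- 15% v 5%: 1.96 × √(0.1750/107) = 7.9 points
- 20% v 10%: 1.96 × √(0.2500/107) = 9.5 points

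| Assumed risks | Difference (points) | Wald 95% CI | Newcombe 95% CI |
|---|---|---|---|
| 10% v 5% | 5 | −2.0 to 12.0 | −2.3 to 12.7 |
| 15% v 5% | 10 | 2.1 to 17.9 | 1.9 to 18.4 |
| 20% v 10% | 10 | 0.5 to 19.5 | 0.4 to 19.6 |

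If the two arms have equal risk, the Newcombe half-width runs from 4.9 points at about 2% to 12.1 at about 30%.

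**Estimate or test.** Power at the two-sided 5% level is about 34% for 5/107 v 11/107 and 48% for 11/107 v 21/107. A hypothesis test would therefore add little. An interval is still informative: in the first row of the table, the data would exclude an excess in the higher-risk arm of more than about 12 points.

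**The case against.** The strongest reply is that this is a preference about reporting and identifies no fault. Descriptive tables are usual for sparse, mixed surgical complications. Section 23.1 leaves detail to the SAP, which could add a risk difference without contradicting the protocol. The prose of section 9.1 names re-rupture and re-operation among the secondary outcomes and puts complications in general among the measures, which matches the split in 23.3.2. If participant counts are published by arm, any reader can work out the interval. A single any-complication figure would also pool swelling with pulmonary embolism and include contralateral graft harvest, which section 21.3 marks as possible only after reconstruction.

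Most of this stands, and it is why the point is minor. It does not remove the case for the change. Table 9.3 does list complications as a secondary outcome, and counts by type do not add up to participants when one person has several events. The proposed figure would sit beside the type table and not replace it.

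A reader might also infer more than the protocol supports:

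- *That complications are the only secondary outcome without a between-arm method.* This is true only of the outcomes named in 23.3.2. Time to return to sport, time to return to work and surgeon confidence have no method named there at all.
- *That the protocol rules out a participant-level count.* Reporting by frequency can include one.
- *That the observed risks will be materially diluted, or the denominators cut, by questionnaire loss.* The 24-month check does centre on readmissions ("Data from readmission events identified will be recorded in the CRF"), and a participant may withdraw record access ("No longer willing to have routine data from the medical record provided to the study"). However, intra-operative and pre-discharge events go on CRFs whether or not a questionnaire comes back, and hospital records are checked at 24 months. The KOOS-4 missing-data rates cannot be carried over to this outcome.

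**Conclusion.** The point holds as an optional improvement and is not an error. Section 23.3.2 plans descriptive figures only for a listed secondary outcome, apart from graft failure and re-operation, although 23.3.1 favours estimates with intervals wherever they can be given. An interval can be computed from data already collected.

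Under the three assumed pairs of risks, which lie between 5% and 20%, the interval would extend about 7 to 9.5 points either side at 107 per arm. These figures rest on assumed risks and full ascertainment, because the protocol states no complication rate.

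It would be wrong to read this as a failure to test a stated hypothesis. Fewer complications is background rationale in section 8, the trial is not sized for it, and no primary inference depends on it. The SAP, which is not at hand, may already provide the estimate.

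**What to change.** Add to section 23.3.2, or settle in the SAP before it is finalised:

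*The number and proportion of participants with at least one intervention-related complication up to 24 months will be reported by randomised arm with an unadjusted risk difference and 95% CI, as estimation and not a hypothesis test. Graft failure and re-operation keep their own survival analysis. A complication that led to re-operation counts under its own type. Continued instability without confirmed graft failure counts as a complication.*

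Keep the type-by-arm table next to this figure and add the Clavien-Dindo grade. The two counting rules are needed because Table 9.3 includes re-operation under complications and section 21.3 lists graft failure and continued instability together.

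The cost is a few sentences and a few lines of code, with no new data, participant burden or change in sample size. Two downsides should be stated with the result. The interval will be wide, and the summary mixes severities and includes one item that can arise only after reconstruction. It should therefore not be shown without the table by type and grade.
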